
In a secondary study to be done in collaboration with the NIDA IRP, participants will also undergo ambulatory monitoring of mood, behavior, and geolocation. The aim is to follow up on prior findings from the IRP that, unlike the general population, people in addiction recovery may experience work as a respite from stress.

2. Objectives

The project will have the following primary and secondary objectives:

Primary Objectives. Assess the effectiveness of the IPS Plus Abstinence-Contingent Wage Supplements in increasing competitive employment and preventing relapse to heroin and cocaine use.

Secondary Objective: Proximal and Distal Risk Factors. Assess the effectiveness of the IPS Plus Abstinence-Contingent Wage Supplements in reducing drug-related risk behaviors (proximal) and reducing family poverty (distal).

Secondary Objective: Post-Intervention Effects. Assess the effectiveness of the IPS Plus Abstinence-Contingent Wage Supplements in promoting long-term drug abstinence and employment and in reducing HIV risk.

Secondary Objective: Economic Analyses. Assess the costs, cost-effectiveness and cost-benefit of IPS Plus Abstinence-Contingent Wage Supplements relative to IPS Only.

Secondary Objective: Ambulatory Monitoring through Geographical Momentary Assessment (GMA). Replicate and extend prior findings that people in addiction recovery may experience work as a respite from stress rather than a stressor. Assess relationships among mood, drug craving, behavior, and activity space in Therapeutic Workplace participants compared to delayed work group, and across time in all participants.

3. Background

Drug addiction can be a chronic problem that can persist for many years and sometimes throughout a person's lifetime (Dennis et al., 2007; McLellan et al., 2000). Treatments can promote drug abstinence in some patients, but relapse is common after treatment (Knapp et al., 2007; Lancaster et al., 2006; Sees et al., 2000; Veilleux et al., 2010). Many individuals achieve periods of drug abstinence that last a year or more, but still relapse (Galai et al., 2003; Shah et al., 2006). The development of enduring solutions to sustain abstinence over many years is perhaps the greatest challenge facing the substance abuse treatment research community. This project seeks to develop a long-term treatment to address the chronic relapsing nature of drug addiction.

Treating Injection Heroin and Cocaine Use in Low-Income, Unemployed Adults

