4. Study Procedures

Procedures for COVID-19

We will complete the remaining assessments without any in person contact. Interviews will be conducted over the phone and when possible we will obtain urine sample results from each participant's clinic. To do that, participants can ask their clinic to send us their urinalysis results. If needed, we will mail a re-loadable credit card to participants.

Recruitment Procedures

Identifying, Screening and Consenting Participants

Participants will be recruited from methadone and buprenorphine programs in Baltimore using procedures that we have used in prior evaluations of the Therapeutic Workplace (Donlin et al., 2008; [name] et al., 2007). First, we will inform staff at methadone and buprenorphine treatment programs in Baltimore about the study and encourage them to refer potential participants to us. Second, we will post flyers and distribute business cards and information sheets with our toll-free number in each of these programs. Copies of the proposed flyer, business card and information sheets are enclosed with this application. Third, we will visit programs and recruit for the study onsite at each program. Fourth, as in our previous studies, participants will have the optional opportunity to earn incentives for referring people who are interested in the study. If a referral attends the initial screening appointment and completes the necessary assessments, the participant who referred the person will receive up to \$20. If a referred person enrolls in the main study, the participant who referred the person will receive up to \$40 for making the referral.

Experimental Design and Groups

Phase 1 Abstinence Initiation and Job Skills Training

All participants will be invited to attend Phase 1 of the Therapeutic Workplace for about 3 months where they can earn up to about \$40 every weekday and provide urine samples every Monday, Wednesday and Friday. To engage participants, both groups will be allowed to earn wages independent of their urinalysis results for the first 5 weeks.

Delayed Work vs. Immediate Work group. To assess the potential value of working in the workplace every weekday, upon enrollment in the study participants will be randomly assigned to a delayed work group or to an immediate work group. The delayed work participants will be paid a daily wage of \$40 for coming to the workplace to sign in and provide a urine sample (on Mondays,

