Wednesdays, and Fridays). The immediate work group will be invited to work in the workplace 4 hrs every weekday, where they can earn about \$10/hr for participating in our job skills training program. This initial period will last for 3 weeks. After the initial three weeks, all participants will be invited to work in the workplace for 4 hours every weekday. GMA data (see below) will be used to compare participants' mood and behavior during weeks that they are at work (Immediate Work group) to weeks where they are not at work (Delayed Work group).

Abstinence initiation. After the 5 week induction period, participants will be required to provide urine samples negative for opiates and cocaine to maintain maximum pay. To allow us to evaluate the effectiveness of the contingencies for opiate and cocaine abstinence in promoting abstinence, we will implement the requirement for opiate-negative and cocaine-negative urine samples after varying durations in the induction period. At the end of Phase 1, participants will be randomly assigned to the study groups.

Vacation days. On quasi-randomly selected work days, all participants will have a paid "vacation" day. During a vacation day, participants will be able to earn their typical pay, but they will not have to attend the workplace and work to earn it. This will enable us to assess how unexpected free time affects mood and behavior. We have used similar paid vacation days to maintain participants' pay during actual holidays, weather emergencies and other workplace closings. GMA data (see below) will be used to compare participants' mood and behavior on days that they are at work (regular work days) to days where they are not at work (vacation days)

Geographical Momentary Assessment (GMA). The GMA-related procedures will occur for 12 weeks of the first 3 months of Phase 1. One week after signing informed consent, all participants will be issued a smartphone for GMA. The one-week delay is to help ensure that smartphones are issued only to participants who intend to return.

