Analyses for the secondary GMA aim. Most of these analyses will be done by [name] group. Like the other repeated measures, the GMA data will be analyzed with longitudinal regression models. [name] group uses mixed models (Proc Mixed and Proc Glimmix in SAS 9.4) to handle within-person correlation and missing data. Tests will be two-sided and p-values <.05 will be considered significant. The main comparisons of interest will be: (a) Between-group comparisons of mood, craving, stress, and other GMA measures during weeks 2-3, when participants have been randomized to immediate versus the delayed work condition. (Waitlist participants who have other employment during weeks 2-3 will be excluded from most of these analyses.) (b) Within-person assessment of changes in those variables in the delayed work group, comparing weeks 2-3 to weeks 5-13. (c) Contrasts in all participants between unannounced vacation days and the corresponding weekdays from a week with no vacation. For comparisons a, b, and c, effect sizes are expected to be fairly large, because work accounted for 20-50% of the variance in mood and craving in a EMA prior study at the NIDA IRP (Epstein and Preston, 2012). We will also assess (d) between-group and within-person differences in GPS-assessed activity space during working and nonworking periods. We have no prior data on that question; those analyses will be exploratory.

Economic Analyses

Our economic evaluation will be done from the provider perspective.

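### Secondary GMA contrast (b) cannot separate the start of work from abstinence-contingent pay or elapsed time, so it should be reported as descriptive (minor)

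*Combined protocol and SAP*

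**What the plan says.** Section 7c, Analyses for the secondary GMA aim, names three main comparisons and an exploratory fourth. Contrast (a) compares the randomised immediate- and delayed-work groups in weeks 2-3. Contrast (c) compares unannounced vacation days with matching weekdays, in all participants. Between them stands "b) Within-person assessment of changes in those variables in the delayed work group, comparing weeks 2-3 to weeks 5-13". GMA tests are two-sided at .05 and use mixed models to handle within-person correlation and missing data. No covariates are listed for any contrast. On size, the section states: "For comparisons a, b, and c, effect sizes are expected to be fairly large, because work accounted for 20-50% of the variance". That percentage is taken from an earlier study and refers to mood and craving.

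The calendar is in section 4, Phase 1:
- **Pay before the contingency:** "both groups will be allowed to earn wages independent of their urinalysis results for the first 5 weeks".
- **Weeks 1-3, delayed group:** "The delayed work participants will be paid a daily wage of" $40 for signing in and giving scheduled samples, without working.
- **From week 4:** "After the initial three weeks, all participants will be invited to work in the workplace for 4 hours every weekday", at about $10 an hour.
- **Contingency:** "After the 5 week induction period, participants will be required to provide urine samples negative for opiates and cocaine to maintain maximum pay". The next sentence staggers that start over differing lengths of induction, with the purpose "To allow us to evaluate the effectiveness of the contingencies for opiate and cocaine abstinence in promoting abstinence". No schedule is given.
- **GMA:** phones are issued one week after consent and GMA runs for 12 weeks, which fits study weeks 2-13.

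**The concern.** Contrast (b) is a before-after comparison within one arm. Between its two periods, three things change together: the group starts to work, maximum pay comes to depend on negative urine samples, and several weeks pass. Mood, stress and craving could respond to any of them. Craving, for instance, could change because participants are now paid to abstain, or because they have settled into the programme.

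The plan does not treat (b) as neutral description. It puts (b) with (a) and (c) in the sentence that explains the expected effect by work, and names no concurrent group, week term or contingency term for it. Section 9 says corroboration under more controlled conditions is needed before treatment or policy recommendations are drawn from the idea that work lowers stress and craving. If (b) is read as a work effect, it could seem to confirm or contradict (a) for reasons unrelated to work.

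**Working it through.** The plan gives no sample size, power or numeric effect for (b), so there is no figure to reproduce. The check is against the plan's own calendar, with weeks counted from enrolment.

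**Contingent weeks.** With the contingency from week 6, the early period (weeks 2, 3) has 0 of 2 contingent weeks. The later period (weeks 5-13) has weeks 6-13, that is 8 of 9 = 0.89. Only week 5 is work without the contingency.

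**Time.** The mean of weeks 5-13 is 9.0 and the mean of weeks 2-3 is 2.5. The gap is 9.0 - 2.5 = 6.5 weeks.

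**Overlap.** Over the 11 weeks used, 8 are work and contingent, 1 is work only, 0 are contingent only and 2 are neither. The correlation of work with nominal contingency is (8×2 - 1×0)/√(9×2×8×3) = 16/20.8 = 0.77. The correlation of work with calendar week is 0.73.

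**Pay level.** About 4 hours × $10 = $40 a day at work, and $40 a day before it. The amount on offer is not what differs; the condition attached to it is.

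**Unknown stagger.** Difference in contingent share (later minus early), by first contingent week:

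| First contingent week | Difference |
|---|---|
| 1 or 2 | 9/9 - 2/2 = 0 |
| 3 | 9/9 - 1/2 = 0.50 |
| 4 or 5 | 1.00 |
| 6 (nominal) | 8/9 = 0.89 |
| 8 | 6/9 = 0.67 |
| 10 | 4/9 = 0.44 |
| 13 | 1/9 = 0.11 |

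Starts from week 3 to week 13 all leave the later period more contingent. A start in week 1 or 2 would remove that difference, but it would contradict the five-week statement. The 6.5-week gap remains in every case.

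**Illustration (effect sizes assumed, none from the documents).** Suppose work has no effect. A contingency effect of 0.2 SD gives an apparent change of 0.2 × 8/9 = 0.18 SD. A drift of 0.01 to 0.02 SD per week adds or subtracts 6.5 × 0.01 = 0.07 to 6.5 × 0.02 = 0.13 SD. Take 60 people in the arm and a change SD of 1, both assumed. The contingency effect alone then makes a paired test at .05 significant with probability Φ(0.178×√60 - 1.96) + Φ(-0.178×√60 - 1.96) = 28%; with 40 people it is 20%.

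**What a concurrent control does.** Write D and I for the delayed and immediate arms. (D later - D early) - (I later - I early) = (I early - D early) - (I later - D later). The first bracket is contrast (a). The second is zero if the immediate arm's earlier work has no lasting effect and contingency starts are alike in both arms. Group x period therefore targets the same effect as (a).

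**Precision, equal arms.**
- Group x period has √2 = 1.41 times the SE of (b).
- A two-arm mixed model (categorical week, assigned work, contingency starts spread evenly over weeks 5-8) has 1.09 to 1.40 times the SE of (b). This assumes a person-level ICC of 0.3 to 0.7 and weekly autocorrelation of 0 to 0.6.
- Restricting the later period to weeks 4-5 gives √[(1/2+1/2)/(1/2+1/9)] = 1.28 times the SE of (b) with independent weekly errors. Week 5 alone gives √[(1/2+1)/(1/2+1/9)] = 1.57 times. With weeks 4-5 the mean gap falls to 4.5 - 2.5 = 2 weeks.

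**The case against.** The plan does not rest a causal claim on (b) alone. Section 4 describes the use of the delayed/immediate design as a comparison of the two groups, which is (a), and the use of vacation days as (c). Section 7c calls (b) only an assessment of within-person change. The section lists no covariates for any contrast, so its silence on a contingency term may be brevity rather than a decision not to adjust. This stands, and it is why the point is minor. It does not remove the problem, because the effect-size sentence includes (b) by letter and gives work as the reason.

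A two-arm model also adds little that is new. Both groups are assigned to work from week 4, so with calendar week in the model the work effect comes from the between-arm difference in weeks 2-3, as in (a). The gain in precision is bought with a no-carryover assumption. This stands too: such a model does not rescue (b), and should be optional.

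A reader might infer that a one-arm contrast contradicts the objective in section 2, which speaks of relationships "compared to delayed work group, and across time in all participants". The documents do not support that. Contrast (c) covers all participants, and only the delayed arm has an assigned no-work period followed by work.

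A reader might also expect the staggered contingency to solve the problem. It could help separate the contingency from time, but its schedule is not given and the analysis of (b) does not use it.

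**Conclusion.** The point holds as a minor one, confined to one contrast in a secondary aim. On the nominal calendar, (b) compares 0 of 2 with 8 of 9 contingent weeks across a mean gap of 6.5 weeks, so a change cannot be assigned to work. This rests on reading week numbers from enrolment and on the five-week statement. The time component holds whatever the stagger.

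The size and direction of the bias are unknown; the SD figures and error rates above only illustrate assumed effects. A reader might go further and infer that the GMA aim cannot show whether work matters, or that the bias favours work. Neither follows. Contrast (a) is randomised, concurrent and nominally before the contingency, contrast (c) compares vacation days with regular workdays, and nothing in the documents fixes a sign. The primary outcomes are not touched.

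**What to change.** 1. In section 7c, report (b) as descriptive, remove it from the sentence that attributes its expected effect to work, and state that causal statements about work rest on (a) and (c). This costs only wording.
2. Optional, if a work effect is wanted from the weeks 2-13 data: take the delayed arm's change minus the concurrent change in the immediate-work arm. Alternatively, fit a two-arm mixed model with calendar week, assigned work status and each participant's actual contingency start as a time-varying term. State that both assume no carryover and then target the same effect as (a). If the arms differed by 0.1 SD in later weeks because of earlier work, the estimate would be off by about 0.1 SD, while (a) would not. If everyone starts the contingency in the same week, it cannot be separated from calendar week, but work still can.
3. Optional sensitivity analysis: in the delayed arm, use only work weeks before that participant's contingency began (nominally weeks 4-5). Show it with and without week 4, which the plan leaves out. It loses precision and still does not remove time.
4. Record each participant's actual contingency start, state whether starts were pre-set or depended on behaviour, and reconcile the five-week and staggered-start statements in section 4.

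The data are already planned; the work is SAP wording and a few extra models.

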
Specific Aim. *Assess the cost-effectiveness of IPS Plus Abstinence-Contingent Wage Supplements.* Separate cost-effectiveness analyses will be conducted for the outcomes of substance use, employment, and drug-related HIV risk behavior. We will assess incremental cost-effectiveness ratio (ICER) by dividing the difference in costs of two interventions by the difference in the effects of the two interventions. The estimated ICER can be interpreted as dollars spent per unit of desired outcomes gained. We expect that IPS Plus Abstinence-Contingent Wage Supplements will yield better ICERs for all three measures.

[figure not shown]
Specific Aim. *Assess the cost-benefit of IPS Plus Abstinence-Contingent Wage Supplements.* We will perform a Cost-Benefit Analysis (CBA) to examine the monetized benefits relative to costs for the two intervention conditions. The economic outcomes are employment, crime, and health care utilization. We expect that IPS plus Wage Supplement will yield greater economic benefits in criminal activity, health care utilization, and employment in the 24-month post enrollment time period relative to its costs than the IPS only condition.

Specific Aim. *Geographical Momentary Assessment.* We will assess collect the four types of ambulatory entries described above (randomly prompted entries and three types of event-related entries), along with time-stamped latitude and longitude data from the smartphone's GPS unit. In some analyses, we will examine the latitude and longitude data in terms of objective information about social disorder in the neighborhoods where they were collected, as we have done in our published work (Epstein et al., 2014).

- c. Statistical plan including sample size justification and interim data analysis.

Power Analysis

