Cost Analysis. We will derive cost estimates of intervention activities following an activity-based approach (Drummond et al., 2005; Gold et al., 1996; [name], [name] et al., 2004; [name] et al., 2005; [name], [name], et al., 2008). The total cost per participant of each intervention condition will be the sum of (1) staff labor costs, (2) costs of building space, (3) costs of the wage supplements; and (4) costs of supplies or materials. The total intervention cost for each participant is the cost per activity multiplied by the number of activities or services received by the participant. Taking the mean across participants in an intervention condition yields the mean per participant cost of that intervention. We will collect data on the costs of the addiction treatment services because the IPS plus Abstinence-Contingent Wage Supplement condition may increase treatment attendance/retention which will affect the overall per-participant costs associated with the intervention. Treatment attendance will be captured in the modified Economic Form 90 AIR/ED. Standard addiction treatment costs will be drawn from the literature (e.g., [name] et al., 2004; Roebuck et al., 2003).

Cost-Effectiveness. Our Cost-Effectiveness Analysis (CEA) methodology (e.g., [name] et al., 1996, 1997, 2008; [name] et al., 2010) will combine the cost estimates described above with associated intervention effectiveness measures. Separate cost-effectiveness analyses will be conducted for substance use, employment, and drug-related HIV risk behavior. The incremental cost-effectiveness ratio (ICER) is calculated by dividing the difference in costs of two alternatives by the difference in effects of the

alternatives. The estimated ICER can be interpreted as dollars spent per unit of desired outcomes gained (e.g., \$300 per day abstinent). To gauge ICER sampling uncertainty, we will calculate the CI via nonparametric bootstrap methods (Indurkha et al., 2001; Briggs et al., 2006). We will also estimate cost-effectiveness acceptability curves (CEAC) using nonparametric bootstrap methods (e.g., [name], et al., 2010; [name] et al., 2008; UKATT Research Team, 2005). The CEACs incorporate the inherent variability of cost and effectiveness estimates and show the probability that a treatment is cost-effective as a function of the policy maker's intrinsic valuation/willingness to pay for the clinical outcome.

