Cost-Benefit. We will perform a Cost-Benefit Analysis to examine the monetized benefits relative to costs for the two intervention conditions. The key economic outcomes are employment, crime, and health care utilization. These outcomes will be assessed through the modified Economic Form 90 AIR/ED. The unit costs to be used in monetizing these economic outcomes will be drawn from various literature and public data sources (e.g., [name] et al, 2010; French et al. 1996; Roman et al., 1998; Cohen et al., 1994).

Sensitivity Analysis. We will conduct sensitivity analyses to assess whether the economic results are affected by changes in model parameters, such as assumptions made in estimating costs. We will perform one-way sensitivity analyses in which we examine the effect of changing one of the model parameters while holding all other parameters constant. We will also perform *n*-way sensitivity analyses in which *n* parameters of the model are varied jointly, holding all other parameters constant.

d. Early stopping rules.

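### The economic evaluation declares a provider perspective, but its cost-benefit analysis counts crime and employment benefits that do not reach the provider, so that comparison belongs to no single perspective

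*Combined protocol and SAP*

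**What the plan says.** Section 7.c, Economic Analyses, opens with a single sentence on perspective: "Our economic evaluation will be done from the provider perspective". It makes no exception for any of the analyses that follow.

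Under Cost Analysis, the cost per participant has four listed components: "1) staff labor costs, (2) costs of building space, (3) costs of the wage supplements; and (4) costs of supplies or materials". A later sentence there adds a further item: "We will collect data on the costs of the addiction treatment services", with standard costs taken from the literature.

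Under Cost-Benefit, the plan states: "The key economic outcomes are employment, crime, and health care utilization". On valuation it says: "The unit costs to be used in monetizing these economic outcomes will be drawn from various literature and public data sources". The purpose is "to examine the monetized benefits relative to costs for the two intervention conditions". In Section 7.b, the matching Specific Aim predicts that the supplement arm "will yield greater economic benefits in criminal activity, health care utilization, and employment in the 24-month post enrollment time period", when benefits are set against costs and compared with IPS Only.

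The Sensitivity Analysis paragraph varies model parameters, one at a time and jointly. It does not name a change of perspective. Nowhere do the documents define *provider* or mention a societal, payer or participant perspective.

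**The concern.** A perspective decides which costs and which benefits count, and it has to be the same on both sides of a cost-benefit comparison. Here the cost side is mostly what the program pays out, while the benefit side is mostly what other parties gain. From the provider's position, crime avoided and wages earned by participants are not returns. From society's position they are, but a cash supplement moves money from program to participant and is conventionally not a net resource cost.

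Cost-benefit is part of a stated secondary objective (Section 2) and carries a directional expectation (Section 7.b). A reader told that the result is from the provider perspective could take it to mean that a provider recovers its outlay through these benefits. The planned analysis cannot show that.

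**Working it through.** **1. The plan's own figure.** Section 10 (Phase 2) gives $8 per hour, 40 hours per week and 52 weeks: 8 x 40 x 52 = $16,640 per participant, which matches the stated maximum. Before employment, Section 4 describes incentives of about $200 per week. Over a full year without a job that is 200 x 52 = $10,400. Since 8 x 40 = $320 per week exceeds $200, $16,640 is the ceiling on these figures.

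**2. Where each item falls.**

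| Item | Source | Falls on |
|---|---|---|
| Staff, space, supplies | 7.c Cost Analysis | Provider |
| Wage supplements | 7.c Cost Analysis | Paid by the provider, received by the participant |
| Addiction treatment | 7.c Cost Analysis | Outside methadone and buprenorphine programs (Section 4, recruitment) |
| Crime | 7.b; 7.c Cost-Benefit | Outside any service provider |
| Employment | 7.b; 7.c Cost-Benefit | Participant; Section 9 adds government and community |
| Health care use | 7.b; 7.c Cost-Benefit | Unclear; the provider only if the term covers a wider health system |

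The cost side is mainly the provider's. At least two of the three benefits are not.

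**3. What each perspective would compute.** Per participant, relative to IPS Only, let S be supplements paid, O other incremental cost, and B the monetized crime, employment and health care benefits, with earnings net of supplements. Assume that no part of B reaches the provider.

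- Provider: -(S + O)
- As written: B - (S + O)
- Societal, supplement as a transfer: B - O

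The as-written result differs from the provider result by B, and from the societal result by S. Differences are used only for clarity. The plan names no form, and a ratio has the same mismatch: B/(S + O) as written against B/O.

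**4. Illustration.** The documents give no value for O or B and no expected S, so every value below is assumed except the $16,640 ceiling. With O = $1,000, results in dollars are:

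| S | Provider | As written: B = 0 | B = 5,000 | B = 15,000 | B = 20,000 |
|---|---|---|---|---|---|
| 2,000 | -3,000 | -3,000 | 2,000 | 12,000 | 17,000 |
| 8,000 | -9,000 | -9,000 | -4,000 | 6,000 | 11,000 |
| 16,640 | -17,640 | -17,640 | -12,640 | -2,640 | 2,360 |
| Societal, any S | | -1,000 | 4,000 | 14,000 | 19,000 |

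The as-written and societal results differ in sign only when O < B < S + O. In this table that happens at S = 8,000 with B = 5,000, and at S = 16,640 with B = 5,000 or 15,000. Elsewhere they agree in sign and differ in size. The table shows that the answer can depend on perspective. It does not predict that it will.

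**The case against.** The best defense is that the perspective sentence was meant for costing. It stands directly before Cost Analysis, and the four listed cost items fit a provider view. On that reading the plan sets program cost beside a list of external benefits, and the only fault is a label that was not limited to costs. This is plausible, but the sentence covers the whole evaluation and nothing narrows it, so even this reading needs the text changed.

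The objection also rightly limits the point. A reader might infer more than the documents support:

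- *That charging the supplement is an error.* Under the declared perspective it is correct, and Section 7.b expects supplements to raise costs. Treating them as a transfer is a convention that applies once a societal view is adopted, and the plan adopts none.
- *That the supplement decides the sign of a net benefit.* The plan speaks of benefits relative to costs and names no net-benefit figure. With no benefit values given, a change of sign appears only under assumed inputs.
- *That $998,400 is at stake* (60 x 16,640, assuming equal arms). This needs every participant in the arm to work 40 verified hours in all 52 weeks at the full rate. Participants enter unemployed, Section 3 reports about 20% working full time after earlier Therapeutic Workplace participation, and Section 4 cuts the rate to $1 per hour after a missed or positive sample.
- *That supplements are counted twice, as a cost and as earnings.* The items of the economic form are not shown, so this is conjecture. For family poverty, Section 7.b already plans results with and without supplement earnings. The cost-benefit text simply has no matching rule.
- *That the whole economic evaluation is compromised.* Cost-effectiveness ratios and acceptability curves relate program cost to clinical and employment outcomes and largely fit the provider view.

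**Conclusion.** The point holds for the cost-benefit analysis alone. The declared perspective and the listed benefits contradict each other in the current text, and no other section reconciles them. This is wrong as written, and more than missing detail: an analyst who follows the plan exactly obtains a comparison that is neither a provider's nor society's. The conclusion is firm for crime and earnings, and less certain for health care use while *provider* stays undefined.

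The documents support one statement of size. The result can differ from a societal one by the supplement actually paid, which cannot exceed $16,640 per participant and will be lower in practice. This assumes that supplements are treated as a transfer in the societal view and are not included in monetized earnings. Whether the cost-benefit conclusion would change cannot be determined. Both primary outcomes and N = 120 are unaffected.

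**What to change.** In Section 7.c, limit the provider perspective to the cost and cost-effectiveness analyses, and declare a societal perspective for the cost-benefit analysis. Within the cost-benefit analysis:

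- show wage supplements and task incentives on a separate line, and exclude them from monetized earnings;
- report the main result with them treated as a transfer (outside net social cost), and a sensitivity analysis with them as a program cost;
- state that addiction treatment already costed under Cost Analysis is not counted again as health care utilization.

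A separate provider-only cost-benefit table is not needed, since it would largely repeat the cost analysis.

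The price is SAP wording and one extra tabulation of data already planned. The present cost list was built mainly for a provider view and may not cover every cost to other parties. Any societal cost items not collected should be listed as a limitation.
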